Due to the aforementioned reasons, we believe that that a web based peer-led intervention to educate the public on dating application risks would be effective and appropriate. In this study, we evaluate the effectiveness of a web-based peer-led intervention to promote safe usage of dating applications among young adults aged 18-27 in Hong Kong. The trial will be conducted in compliance with the protocol, GCP, and the applicable regulatory requirements.

Trial Objectives and Purpose

Aim: To promote safe usage of dating applications among young adults in Hong Kong

Objectives

- To evaluate the effectiveness of a web-based, peer-led intervention in:
 - Providing appropriate and reliable information about dating applications to young adults in Hong Kong
 - Increasing the awareness of dating application associated risks and benefits among young adults in Hong Kong
 - Improving the attitudes towards risk perception and the safe usage of dating applications among young adults in Hong Kong

• Promoting behavioral skills related to the safe usage of dating applications in young adults in Hong Kong, specifically in preventing and handling negative experiences associated with dating applications

Trial Design

Study design

The study will use an open-labeled randomized control trial design with one intervention arm and one control. The control will have access to an online resource with similar interactive elements and time usage on a different topic. Both arms will complete the baseline and final questionnaire. There will not be any blinding as it is an open labeled study but participants will be randomly assigned to the intervention or control arm with a randomization software. Students in the Yijin program may be randomized by clusters to minimize the chance of contamination.

Intervention

The intervention is a web-based resource including text content, 4 videos, a scenario game and a risk assessment. The program can be accessed on both phones and other mobile devices such as smart phones and ipads. The topics of each segment is listed below:

Video 1: Introduction of the theme that meeting people on dating apps and meeting friends in real life present the same risks. The focus is that users should not have assumptions when meeting people in either context. This video also touches upon social expectations and pressures to pay for dates, leading to potential risk of falling victim to monetary scams.

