Delivery of Intervention

There will be two modes of intervention delivery. In the educational settings, a research assistant and a member of the investigative team will attend a class session to provide a quick introduction to the study and deliver the web-based resource. Participants will be asked to bring their computers or phones and will be provided with the link to the intervention during a class session. Participants will be told that participation is voluntary and that their participation will not have any effect on their grades for the class.

For participants recruited from NGOs, the intervention will be delivered electronically. An email containing the same information as presented by the investigative team member in the educational settings will be sent to the participants along with the access link to the intervention.

Consent for participants in educational settings will be obtained with a written consent form. The investigative team will pass out the consent forms to the participants after the brief introduction of the study and before the delivery of the intervention content. Participants will be given time to read over the information and the signed consent form will be collected by the investigative team. There may be a possibility that a few students in the Yijin Program are under 18 as the program accepts students who just graduated from secondary 6. If this occurs and the student would like to participate, the school will provide consent for the student *in loco parentis*, or in the place of the parent or legal guardian.

Participants recruited from NGOs will be sent an electronic consent form. The online consent form is made on the program Survey Gizmo and participants can access this form either from a share link or through a QR code. Information on the study is provided in the online form and participants are prompted to tick the necessary items to indicate their understanding and agreement. Participants will then be able to sign the form electronically with their computer mouse or touch screen. The age range for recruitment for NGOs will be 18-27 therefore there should not be anyone below 18.

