The primary endpoint will be 1 month after the delivery of the intervention. Students will fill out a baseline questionnaire before the delivery of the intervention and an immediate post questionnaire. 1 month later, students will access a follow-up questionnaire via HKU Survey Gizmo, a secure survey tool to ensure all data is kept confidential. The details of the delivery method of the follow-questionnaire will be discussed with the college's staff. Research staff may attend a special session or class to delivery the follow-up questionnaire. Another option is to have teachers deliver the follow up questionnaire. The follow-up questionnaire will be online hence participants will be able to access it on their computers, phones, or other mobile devices. Participants are estimated to participant in the trial for no longer than 4 months. Participants are allowed to withdraw from the study at any point in time without any criterion.

Selection and Withdrawal of Subjects

Inclusion criteria

- Aged 17-27
- Able to read and understand Chinese
- Able to provide an active email

Exclusion criteria

- People who have a physical impediment in which they cannot access the material in the intervention

Participants are allowed to withdraw from the study at any point in time without any criterion. We will utilize the "intention to treat" approach to deal with subjects withdrawn.

Treatment of Subjects

The intervention is a web based intervention and will not involve any medical treatments, drugs, or pharmaceuticals. The route of administration is access through any device that can access web-based content and the dosage is one visit.

Assessment of Efficacy

Evaluation will be done with an online survey tool called HKU Survey Gizmo. There will be a pre questionnaire containing baseline demographics and other questions concerning dating application usage. The participants will be given 30-45 minutes to access the program. Following that, the participants will be given a post questionnaire. 1 month later, the participants will be asked to fill in a follow up questionnaire.

Assessment of Safety

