Participants will be given contact information to a dedicated staff if they have any questions of concerns regarding the study and their participation in the study. Additional psychological risk may occur as the study involves bringing up sensitive topics such as risky sexual behavior and personal data, to minimize this risk, participants will be ensured that their information is protected with the utmost care and that all their gathered information will only be used for researched purposes. Any adverse events will be recorded.

Statistics

Sample size calculation

The sample size was be calculated with the following components:

- α (two-tailed) of 0.05
- $\bullet \qquad \beta = 0.8$
- Obtained from a study with a peer-led safe sex online intervention for Hong Kong adolescents aged <25 (19)
 - o Standard deviation: 0.52
 - o Effect size: 0.21

Attrition rate: 15% in online studies (20, 21)

112 people per intervention arm

Data Analysis

Data will be analyzed using SPSS. Descriptive statistics will be carried out analyze the demographics of the target population. Differences in baseline demographic characteristics between the intervention and control group will be assessed using chi-squared tests.

For outcome evaluation, paired t-tests will be used to examine within group outcome changes. For the primary outcome that is a score, linear regression will be used to evaluate the difference between the control and intervention group.

Independent t-tests will be carried out to evaluate the score change within group and also between groups. The outcome difference at baseline and at follow-up will also be evaluated with linear regression.

Direct Access to Source Data/Documents

The investigator/institution will permit trial-related monitoring, audits, IRB/IEC review, regulatory inspections, providing direct access to source data/documents.

Quality Control and Quality Assurance

Ethics

Major ethical issues involve asking about sensitive information regarding risky sex behaviors, users' privacy, and legal issues. Participants will be ensured by the project's researchers that their information is kept strictly confidential. Researchers will also ensure that participants understand the purpose and procedure of every step of the project and participants will be provided with a contact for whenever they have any questions or concerns. Patients also understand that they are allowed to withdraw at any given point of the study.

Data Handling and Record Keeping

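### The only safeguard against contamination is optional and partial, and the documents describe neither arm-restricted access to the dating-app site nor any measure of control exposure before the 1-month endpoint

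*Protocol*

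**What the plan says.** The trial is open-label with two arms, and participants are assigned at random by software (Protocol, Study design). The same section adds: "Students in the Yijin program may be randomized by clusters to minimize the chance of contamination". That is the only mention of contamination in either document. It does not say whether a cluster is a class, a campus or something else, and it does not commit to clustering.

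On delivery, the protocol says of the educational settings: "Participants will be asked to bring their computers or phones and will be provided with the link to the intervention during a class session" (Delivery of Intervention). NGO recruits get an email with the study information and the access link (same section). Controls are sent links to a government exercise website (Control); no place or time is given for this.

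On access: "The route of administration is access through any device that can access web-based content and the dosage is one visit" (Treatment of Subjects). Participants have 30-45 minutes for the program (Assessment of Efficacy). On timing: "The primary endpoint will be 1 month after the delivery of the intervention" (Delivery of Intervention).

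The protocol handles withdrawals by intention to treat, and the SAP adopts intention to treat with last observation carried forward. Neither document describes a login, an arm-specific link, an instruction not to share, a question about exposure to the other arm's resource, or an analysis of such exposure.

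**The concern.** Individual assignment is the default, so students of both arms may sit in one class when the dating-app link is given out. An emailed link can be forwarded between NGO recruits. A month then passes before the primary outcome is measured. The protocol recognises the risk but does not commit to anything that would contain it.

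A control who works through the dating-app site before the 1-month questionnaire has received some of the tested intervention but is still analysed as a control. The control mean moves towards the intervention mean and the estimated effect shrinks. This bias is towards no effect, so it would not create a false benefit. The loss is one of interpretation: without a record of exposure, a null result could mean that the resource does not work or that controls also used it. A record that was not planned cannot be reliably rebuilt once the 1-month data are in.

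**Working it through.** **Inputs** (Protocol, Sample size calculation): "α (two-tailed) of 0.05"; power 0.80 (printed as β = 0.8, read here as power); "Standard deviation: 0.52"; "Effect size: 0.21", read as a raw mean difference; 15% attrition; 112 per arm.

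**Step 1. Reproduce the planned size.** n per arm = 2 × [0.52 × (1.960 + 0.842) / 0.21]² = 96.3, rounded up to 97. Then 97 × 1.15 = 111.6, rounded up to 112, which matches. (Dividing by 0.85 instead gives 114.1, so 115.) Reading 0.21 as a standardised effect would give 356 per arm before attrition, so the raw reading is the one that fits. No allowance for crossover enters the calculation.

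**Step 2. Numbers with 1-month data.** 112 × 0.85 = 95.2, taken as 95 per arm.

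**Step 3. Dilution.** Let c be the share of controls exposed and f the fraction of the full effect each of them receives. The expected arm difference is 0.21 × (1 − c × f). The documents give neither c nor f, so both are assumptions. Setting f = 1 gives the upper bound on the loss.

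**Step 4. Power.** Two-sample t-test, two-sided 0.05, SD 0.52, f = 1:

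| Controls exposed (c) | Expected difference | Power, 95 per arm | Power, 112 per arm |
|---|---|---|---|
| 0% | 0.210 | 79% | 85% |
| 5% | 0.1995 | 75% | 82% |
| 10% | 0.189 | 70% | 77% |
| 20% | 0.168 | 60% | 67% |

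The last column applies if last observation carried forward keeps all 112 per arm in the analysis and the carried values hold the same effect and SD. That is optimistic, so the column is an upper limit on power.

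**Step 5. Partial exposure.** With f = 0.5, the loss depends on half of c. At 95 per arm, 10% exposed gives 0.21 × (1 − 0.05) = 0.1995 and power of 75%; 20% exposed gives 0.21 × (1 − 0.10) = 0.189 and power of 70%.

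**The case against.** The strongest reply is that most of this rests on silence. Several stronger readings are tempting, and the documents do not support them.

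- A reader might infer that both arms' links are handed out in the same room. The class-session sentence mentions only the intervention link, and the Control section does not say where or when controls get theirs. If whole classes become the clusters, the arms would not share a class at all.
- A reader might infer that the site stays open for the month, or that no log or question exists. Neither is stated. The follow-up questionnaire is not in the documents, and the phrase about devices concerns hardware, not who may enter. What can be said is that these controls are not described.
- A reader might argue that repeat visits by intervention participants distort the result, given the single-visit dosage. Under intention to treat they do not bias the comparison; they affect only how the tested exposure is described.

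It is also fair to say that Yijin is the only educational programme named, so the clustering option may cover the whole classroom route, and that nothing shows NGO recruits know one another. The exposure rates have no source, a control opening a forwarded link may see only part of the content, and the SAP names a Mann-Whitney test and baseline-adjusted regression, not the t-test used here.

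All of this limits the size and certainty of the loss. It leaves the gap in place: the one safeguard is optional and undefined, it does not reach NGO recruits, and neither arm-restricted access nor measurement of control exposure is described.

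**Conclusion.** The point holds as a gap in safeguards and measurement, not as an established loss. The protocol identifies contamination, makes its only countermeasure optional and undefined, and describes no way to keep controls out of the dating-app site or to learn whether they entered it before the 1-month endpoint.

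The possible cost is a fall in power from about 79% to 70% at 10% exposure and 60% at 20%. This assumes 95 per arm, an SD of 0.52, a planned raw difference of 0.21, and the full effect in each exposed control. It is an upper bound at each assumed rate: if exposed controls get half the effect, the figures at 10% and 20% are 75% and 70%. If all 112 per arm are analysed, power starts near 85% and falls to 77% and 67%. The true rate is unknown, which is the reason to measure it. The remedy is cheap, so the change should be made.

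**What to change.** In Delivery of Intervention, replace the shared link with a participant-specific, arm-restricted link or code, sent to the active email that the inclusion criteria already require. Controls should not be able to open the dating-app site until their 1-month questionnaire is in.

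Add one item to the 1-month questionnaire, in both arms, asking whether the participant saw the other arm's resource. State in the SAP that the proportion of controls exposed will be reported. Keep intention to treat as the primary analysis.

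The cost is minor set-up work and one extra question, with no added participants. If openings are logged, the log should fall under the trial's existing confidentiality terms, because the protocol lists privacy among its main ethical issues.

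Closing the site to intervention participants for the month is not part of this change. Video 4 holds steps and resources for people who have had a negative experience, and restricting controls alone is enough for the purpose.

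### NGO recruits can receive the arm-revealing access link before consent and baseline are secured, and in neither setting is the timing of allocation stated

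*Protocol*

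**What the plan says.** The Protocol's Delivery of Intervention section describes two routes.

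- **Classes.** Staff introduce the study in person. Consent forms are handed out "after the brief introduction of the study and before the delivery of the intervention content". On the questionnaires, "Students will fill out a baseline questionnaire before the delivery of the intervention and an immediate post questionnaire".
- **NGOs.** An email repeats what staff say in class and is sent "along with the access link to the intervention". Consent is described separately: "Participants recruited from NGOs will be sent an electronic consent form", which is opened from its own link or QR code and contains its own study information.

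On allocation, the Study design section says that "participants will be randomly assigned to the intervention or control arm with a randomization software", with no blinding, and that "Students in the Yijin program may be randomized by clusters to minimize the chance of contamination". It requires a baseline questionnaire in both arms. The Control section has control participants sent links to a government exercise website. Assessment of Efficacy lists, for participants in general, a pre-questionnaire, then a session of 30 to 45 minutes with the program, then a post-questionnaire. The SAP does not discuss the order of consent, baseline, allocation and access.

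**The concern.** Consent and baseline are only safe from the influence of allocation if both are complete before the arm is known. In the NGO route the item that reveals the arm travels with the introduction, and nobody is present to see what the recruit opens first. In the class route the content is protected, but knowledge of the arm may not be.

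Two things are at stake. One is selective entry. The control topic, exercise, has nothing to do with dating applications, so willingness to join could differ between people who know which site they will get, and the groups enrolled would then no longer be comparable by randomisation. The other is a contaminated baseline: someone who has looked at the content before answering the pre-questionnaire may already have moved on the outcome. The content also includes sensitive material (Video 4 deals with sexual assault), so access before consent is an ethical matter as well as a statistical one.

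**Working it through.** The plan gives no figure on this point, so the check is mainly a comparison of the two routes.

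| Step | Classes | NGOs |
|---|---|---|
| Introduction | In person, before consent | By email, with the access link |
| Consent | After introduction, before content | Separate e-form; place in the sequence not stated |
| Baseline | Before delivery (sentence about students) | General order only: pre-questionnaire, then access |
| Supervision | Staff in the room | None described |
| Time of allocation | Not stated | Not stated |
| Concealment or release step | Not stated | Not stated |

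**What the email stands for.** Its content is defined as the class introduction. In class that introduction comes before consent: "The investigative team will pass out the consent forms to the participants after the brief introduction of the study". The email therefore fills the pre-consent slot, yet it also carries the link.

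**Whether the link shows the arm.** The intervention is the trial's own web resource, and controls are sent links to a different website. Anyone who opens the link sees the arm. If the emailed link is specific to the arm, allocation must have been made before the email went out.

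**Whether anything blocks early access.** Three statements could do so: the baseline-first sentence about students, the requirement for a baseline in both arms, and the general order in Assessment of Efficacy. Each says what should be completed, and two of them give an order. None makes a signed form or a submitted baseline a condition for the link to work.

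**Classes.** Consent precedes content, and baseline precedes delivery, so content is held back. The missing item is when the arm is decided and who knows it. If a Yijin class is randomised as a unit before the session, the staff who introduce the study and collect consent could already know its arm.

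**Effect on the analyses.** Let *p* be the share of the intervention arm that sees the content before baseline, *g* the mean gain already present in their baseline scores, *δ* the difference expected otherwise, and *b* the slope of follow-up on baseline, with 0 < *b* < 1. Suppose that follow-up scores do not depend on when the content was first opened. The intervention arm's baseline mean then rises by *pg*, and the expected differences are:

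- change scores (Protocol, Data Analysis): *δ* − *pg*
- baseline-adjusted model (SAP, Statistical Methods): *δ* − *b·pg*
- follow-up scores alone, as in the SAP's Mann-Whitney test if it is run on raw scores: *δ*

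Change-score effects shrink most, adjusted effects less, and raw follow-up comparisons not at all. Selective entry is different: it could bias all three, in a direction that cannot be predicted. The documents give no value for *p*, *g* or *b*, nor the share of the sample that comes from NGOs, on which *p* depends.

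**The case against.** The best reply is that the plan does give an order. Assessment of Efficacy places the pre-questionnaire before access for all participants, so early access would be a departure from the plan and not part of its design. The email goes to people already described as recruited from NGOs, and because the e-consent form carries its own study information, it could well be sent and signed before the email. The consent form was not available for this check and may set out a sequence. Any baseline contamination would bias towards no effect, and it would not touch a test on raw follow-up scores.

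Much of this stands. It shows that early access is permitted, not that it happens. It does not close the gap, because an intended order is not a control when participants are remote and the link arrives with the introduction. That the trial is open label is no answer either: keeping the allocation concealed until enrolment and baseline is separate from blinding afterwards.

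A reader might infer that class allocation is known before consent. The documents do not say so; they are silent on its timing, and clustering is only an option. A reader might also infer that an open link lets controls reach the intervention. Nothing says whether links are shared, individual or protected by a password, and forwarding could equally happen after consent, so that is a separate question.

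**Conclusion.** The point holds in a limited form. For NGO recruits, the stated procedure puts the arm-revealing link in the introduction email and does not make consent or baseline a condition of access. For both routes, the Protocol does not say when allocation is generated or revealed, or how it is concealed until then. Class content is adequately protected; class allocation is simply not addressed.

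The consequences are possible selective entry and possible contamination of baseline scores. The direction of the second rests on the content raising scores and on some recruits opening it early. It is tempting to attach a loss of power to this, but the documents give neither the NGO share nor any rate of early opening, so such a figure would rest on invented inputs and would apply to change scores only. The size is unknown. This should be corrected because it is a weakness in a stated procedure that is cheap to remove; it is not a fatal flaw.

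**What to change.** 1. Take the access link out of the NGO introduction email.
2. In Survey Gizmo, already used for e-consent and the questionnaires, require this sequence for NGO recruits: signed e-consent, completed baseline, randomisation, and only then display of the arm-specific link.
3. In classes, open the individual or class allocation only after consent and baseline have been collected, following a neutral introduction that is identical in both arms.
4. State in the Protocol, for each route, when allocation is generated, who holds it and when it is revealed.

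The cost is survey set-up and a few sentences of Protocol text, with no extra staff or visits. The one drawback is an additional online step for NGO recruits.

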Video 2: This video provides a specific example of the discrepancies in behavior in real life vs. when using dating apps. The situation is that one may be less alert when speaking to a stranger on an application.

Video 3: This video provides another example of the risks associated with using dating applications and how this compares to behavior in real life.

Video 4: This video is about the legal issues and risk of sexual assault. This video will also provide information on the steps to take following a negative experience and the available resources.

Scenario game: Participants will make a personalized profile and choose their app at the start of the game. They will then start conversation to start the game and go through a series of situations where they can pick between 5 choices. With a preset algorithm, the choices that the users make will ultimately get them to a certain outcome.

Topics that are explored in the game include: unsafe sexual behaviors, scams, leakage of personal data, intimate photos, and secret photographs.

Risk assessment: A 14-item risk assessment will generate an overall score for participants to infer of their level of risk in using dating applications.

Control

The control group will be the "Health Exercise for all" campaign website by the Hong Kong Government (18). The website provides information for types of exercises that are suitable for all ages and at different settings such as the workplace. The website provides informational pamphlets in PDF format, instructional videos on how to carry out different exercises, and interactive games (18).

The control website begins with an introduction regarding the background of the campaign and it's aims. Contact information for relevant offices for enquiry are provided. The campaign includes nine virtual classes that include 1) Introduction, 2) Points of Note and Exercise Guide and a set of videos of the exercise demonstrations. Videos range from 20 seconds to 10 minutes. Participants in the control group will be sent links to the virtual classes with instructions on which time matched video to watch. The website provides eight different interactive games such as "Calorie Restaurant", "Do I have a big tummy", and "I want to be more active". The "I want to be more active" game is most similar to the scenario game developed in the dating application intervention with seven questions to determine whether one is suitable to engaging is more active athletic activities.

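### The protocol foresees psychological distress, but neither document describes asking participants about it or counting it by arm, so a low count would say little about safety

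*Protocol*

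**What the plan says.** The protocol's Assessment of Safety section names one harm: "Additional psychological risk may occur as the study involves bringing up sensitive topics such as risky sexual behavior and personal data". The mitigation attached to it is confidentiality: "to minimize this risk, participants will be ensured that their information is protected with the utmost care". The section also offers a contact ("Participants will be given contact information to a dedicated staff if they have any questions of concerns regarding the study"), which the Ethics section repeats for all participants: "participants will be provided with a contact for whenever they have any questions or concerns". Ethics adds that procedures will be explained and that participants may withdraw. On collection, the full text is "Any adverse events will be recorded". There is no definition of an event, no question or instrument, no time window and no summary by arm. The SAP's Statistical Methods section has no safety analysis.

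Ethics lists asking about sensitive matters as a major issue. Trial Design makes clear that questionnaires are not confined to the intervention arm: "Both arms will complete the baseline and final questionnaire". Their items are not reproduced.

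Under Intervention, Video 4 deals with legal issues and sexual assault: "This video will also provide information on the steps to take following a negative experience and the available resources". The control is a government exercise campaign: "Participants in the control group will be sent links to the virtual classes with instructions on which time matched video to watch". No equivalent resource information is described for controls.

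Under Delivery of Intervention, study staff attend the class session in educational settings, while NGO participants receive everything electronically. The 1-month questionnaire for students may be delivered by research staff or by teachers.

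**The concern.** The sponsor has identified a specific harm, but the measures described do not detect it. Confidentiality protects data; it neither reveals nor relieves distress. A contact for questions reaches only those who choose to use it. Raising distress in a classroom, possibly with a teacher handing out the follow-up questionnaire, may be hard, and a participant reached by email has no staff member present at all.

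The exposure is not trivial. The protocol's own background reports more sexual abuse among dating-application users than among non-users, so people with such histories can be expected in both arms. The intervention adds content on assault, intimate photos and secret photography, so true distress could differ by arm, and a count by arm would be worth having.

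At stake is the meaning of a small number. If events are not asked for and few are recorded, the trial cannot distinguish a resource that upsets nobody from a collection method that hears from few. The efficacy analysis is not affected.

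**Working it through.** **The denominator.** The documents state no safety figure. The only relevant number is 112 per arm, from Sample size calculation, with inputs two-sided α 0.05, power 0.8 (labelled β), SD 0.52, difference 0.21 (read as a raw mean difference) and attrition 15%.

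- n = 2 × 0.52² × (1.960 + 0.842)² / 0.21² = 96.3, so 97 per arm.
- 97 × 1.15 = 111.6, so 112. The stated figure reproduces. (97 / 0.85 gives 115; that does not bear on this point.)

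**Assumptions.** Let p be the true proportion distressed and c the share of those events that gets recorded. Neither is in the documents, so both are shown over a range.

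**Chance of recording no event in an arm**, (1 − p·c)^112, with expected recorded events 112·p·c in brackets:

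| p | c = 1 | c = 0.5 | c = 0.25 | c = 0.1 |
|---|---|---|---|---|
| 2% | 10% (2.2) | 32% (1.1) | 57% (0.6) | 80% (0.2) |
| 5% | 0.3% (5.6) | 6% (2.8) | 24% (1.4) | 57% (0.6) |
| 10% | <0.1% (11.2) | 0.3% (5.6) | 6% (2.8) | 32% (1.1) |

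**What a zero count would rule out.** This needs no assumption about p. With no recorded event among 112, the one-sided 95% upper limit for the recorded rate is 1 − 0.05^(1/112) = 2.6%. The limit for the true rate is that figure divided by c: 2.6% at full capture, 5.3% at half, 10.6% at a quarter, 26% at a tenth. With c unknown, zero events sets no usable limit.

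**Comparison between arms.** Take true rates of 15% and 5%, also assumed.

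- If c is the same in both arms, the ratio of recorded rates stays (0.15c)/(0.05c) = 3.
- What falls is power. With p̄ the mean of the two recorded rates, power = Φ{[|p₁ − p₂| − 1.96·√(2p̄(1 − p̄)/112)] / √([p₁(1 − p₁) + p₂(1 − p₂)]/112)}. This gives 71% at c = 1, 40% at c = 0.5 and 22% at c = 0.25.
- If c differs, say 50% in one arm and 25% in the other with equal true rates, the recorded ratio is 0.50/0.25 = 2, where the true ratio is 1.

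Low but equal capture costs precision; only unequal capture biases the comparison.

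**The case against.** The case against is substantial and narrows the point.

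- A reader might infer that an event is captured only when a participant contacts staff. The text does not say so. The recording sentence is not limited to one route, staff attend class sessions and may attend the follow-up session, and a distress item could already be among the questionnaire items, which are not shown. What remains is that no document tells anyone to ask.
- A reader might infer that harm cannot be compared between arms. That does not follow. The staff contact goes to all participants without distinction by arm, and unequal capture is not shown. Open-label delivery makes it conceivable, no more.
- A reader might take Video 4's absence in controls as the cause of the problem. Video 4 is randomised content serving a stated objective (handling negative experiences). It concerns dating-application harm, not questionnaire distress, and it is not a reporting channel. Keeping it from controls until the outcome is recorded is the trial's contrast. That controls are never described as receiving its resource information is a separate, smaller gap in support.
- Nor do the documents say that controls are asked about their own negative experiences.
- This is a one-visit web resource with voluntary participation and free withdrawal, and no objective or analysis concerns safety. That limits the severity. It does not explain why a harm the protocol names goes unmeasured.
- The capture shares are assumed, and choosing a low one builds in the result. This is correct: at half capture and a 5% true rate, the chance of an empty count is only 6%.

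**Conclusion.** The point holds in limited form. The protocol names psychological risk, yet the collection it describes is passive and neither document plans a summary by arm. Distress may be under-counted, with NGO participants the likeliest to be missed because no staff attendance is described for them. A low or zero count would therefore be weak evidence of safety.

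How large the under-count would be cannot be derived. The figures above are illustrations over assumed rates, and the chance of an empty count in an arm runs from under 1% to 80% across them. It would be tempting to predict almost no adverse events whatever happens; the documents do not support that, since it depends wholly on an assumed low capture share.

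The conclusion assumes that the questionnaires do not already solicit distress. If they do, a sentence saying so would answer the collection part, leaving the summary by arm and the information for controls. The change should be made because it improves participant safety at very small cost and leaves the randomised contrast intact.

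**What to change.** In Assessment of Safety:

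- Add one distress or adverse-event item, worded identically in both arms, after the outcome items of the 1-month questionnaire, with an optional request for staff contact.
- Add the same item to the immediate post questionnaire if the sponsor accepts a small chance that the prompt, or a staff contact following it, influences 1-month answers. Placing it last protects only the questionnaire it sits in; the primary endpoint comes a month later. The prompt would be the same in both arms.
- Show the staff contact on the closing page of every questionnaire.
- Give controls the resource information from Video 4 after their 1-month outcome is recorded.

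In the SAP, add a descriptive table of counts by arm, with the number who answered the item as denominator. No test is needed.

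The cost is one extra item per questionnaire, a closing page, a small ethics amendment and some contact requests to the staff member already designated. The item will not reach everyone: at the planned 15% attrition, about 112 × 0.85 = 95 per arm would answer at 1 month, and anyone who left because of distress would be missed there. That is the main argument for asking at the immediate post questionnaire as well.
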